Counseling: Counseling: Counseling will consist of one-on-one sessions with a health coach who will provide MIND+SOUL diet continued education and on-going support throughout the diet intervention. This support will consist of education and recommendations specific to the participant's needs, preferences, and local context. The health coach will help participant set dietary goals in relation to the MIND+SOUL diet, help participants develop an action plan for certain situations (i.e. holiday parties, vacations), and provide encouragement in regards to the formation of healthy eating habits. Zoom conference calls will occur bi-weekly for 12-weeks. Each Zoom conference (6 total per participant) is anticipated to last 15-20 minutes each time, with exception to the first Zoom conference call which is anticipated to up to 30 minutes.

Financial support: To improve adherence to the MIND+SOUL diet each participant will receive weekly groceries worth up to \$50 per week (total average of \$600) that will be provided to each participant for 12-weeks. Groceries will be limited to foods within the 10 distinct food groups of the MIND+SOUL diet. These foods will be selected from each week from a community supermarket.

C. Sample size, statistical methods, and power calculation

Single arm: Participants will be in a single arm trial using 3 cohorts (cohort 1 – 10 people, cohort 2 – 10 people, cohort 3 – 10 people). Rationale: Use of a single arm trial will allow for assessment of feasibility and acceptability of the MIND+SOUL diet. Additionally, use of 3 cohort will allow for an opportunity to make revisions between each cohort to further enhance feasibility and acceptability of the MIND+SOUL diet.

Individuals deemed eligible will be placed into 1 of 3 cohort.

Sample Size: A total of 30 participants will be enrolled in the pilot study. Cohort 1 will consist of 10 participants, cohort 2 will consist of 10 people, and cohort 3 will consist of 10 people.

D. Subject Criteria:**1. Inclusion Criteria**

- a. Identify as African American or Black
- b. Age 55 and older
- c. English Speaking
- d. 1 or more of the following CVD risk factors (high blood pressure, high cholesterol, controlled type 2 diabetes overweight/obesity with a BMI of 25 or more as calculated from weight and height at baseline visit)
- e. Cognitively Normal with an AD8 <2 (normal cognition)

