- f. Females of child-bearing potential (i.e., pre-menopausal) must have a negative urine pregnancy test at the screening visit and must agree to use of contraception throughout the trial. The approved methods of contraception are abstinence, the consistent use of an approved oral contraceptive (birth control pill or "the pill"), an intrauterine device (IUD), hormonal implants, contraceptive injection, double barrier method (diaphragm with spermicidal gel or condom with contraceptive foam).

2. Exclusion Criteria

- a. No CVD risk factors
- b. AD8 equal to or greater than 2
- c. Diagnosed with type 1 diabetes
- d. Uncontrolled diabetes type 1 or type 2
- e. Existing diet plan that subject is unable to pause during trial
- f. No internet connection
- g. Uncontrolled hypertension, by history, or as indicated by sitting systolic blood pressure >165 mmHg or diastolic blood pressure >95 mmHg at the baseline visit. If an initial blood pressure reading is higher than this, an additional attempt (at this visit or on another day) could be used before excluding a patient for uncontrolled hypertension
- h. Neurological diseases that impact cognition
- i. Other medical conditions likely to be negatively impacted by a diet change or that could confound the study data (i.e. Celiac Disease, Ulcerative Colitis)
- j. Unable or unwilling to provide written consent
- k. PI determination that study is unsafe or unsuitable for the participant
- l. Active depression as determined by a score of 5 or above on the PHQ9 and deemed to be clinically significant by the medical monitor

3. Withdraw/Termination criteria:

- a. There is no withdraw or termination criteria
- b. Participants are allowed to participate in other observational studies during their enrollment period, but not interventional trials

Total enrollment is anticipated to last between 3-4 months total, with 1-1.5 months of recruitment per cohort.

E. Specific methods and techniques used throughout the study

This study will require two study visits. Outcome data will be collected at baseline and at the 12 week mark (+/- 2 weeks). The total time commitment for visit 1 is 2.5 hours and visit 2 is 2.5 hours.

Visit 1 – Baseline Evaluation

Estimated duration: 2.5 hours

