Check for Adverse Events (5 minutes): At the Week 12 Visit, study staff will query the participant for any new health conditions that may have arisen since the Baseline Visit. Adverse event information will be collected and recorded as described in section K. Assessment of Subject Safety and Development of a Data and Safety Monitoring Plan below.

Acceptability surveys (30 minutes): Participants will complete 2 acceptability surveys at the 12 weeks (\pm 2 weeks). The first survey is a structured survey using 5-point Likert Scale (domains: affective attitude (how an participant feels about the MIND+SOUL intervention), burden (perceived amount of effort required to participate in the MIND+SOUL intervention), ethicality (extent to which the intervention has good fit with the participants value system), perceived effectiveness (extent to which the intervention is perceived as likely to achieve its purpose), and self-efficacy (participants confidence that they can perform the behaviors required to participate in the intervention). The second survey is a satisfaction with MIND+SOUL diet survey using a visual analog scale.

Post Intervention

Focus Group: Upon completion of cohort 1 and cohort 2 a subset of participants will participate in one of two focus group discussions to further capture feasibility and acceptability of the MIND+SOUL intervention. We will hold two 30-minute virtual semi-structured focus group discussions (n=2-3 participants per focus group) to capture feasibility and acceptability of MIND+SOUL intervention. Focus group participants will receive a \$25 Visa gift card for their participation.

	Baseline Visit (-30 Days)	Week 1-Week 6 (Day 0)	Week 7-Week 11	Week 12 Visit (+/- 2 weeks)
Informed Consent	X			
Urine pregnancy test, as needed	X			
Medical History/ Current medications	X			
Blood Pressure	X			X
Verification of Eligibility	X			
DXA Scan	X			X
Height / Weight/Waist circumference	X			X
Blood Draw	X			X
NHANES Dietary Screener Questionnaire	X			X
Skin Carotenoid Content	X			X
NIH Toolbox Cognitive Battery	X			X
Acceptability Surveys (structured survey and Visual Analog Scale)				X
Adverse Event Check				X
Skill Building Health Education/Cooking Classes 1x week		X		
Health Coaching 2x Month		x	x	

Testing Results

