Research results will be shared with the community through a powerpoint or poster presentation at a conference and via a letter with a summary of study findings, which will be mailed to participants at the end of the study. Further, study findings will be posted on social media outlets such as Facebook and Twitter. To sustain a research relationship with the AA community we plan to continue to pursue collaborative projects aimed specifically towards focusing on the needs for the community. Upon completion of this project we plan to expand this project on a larger scale by designing an AA culturally MIND+SOUL diet intervention for implementation as a future R01 scale clinical trial.

K. Assessment of Subject Safety and Development of a Data and Safety Monitoring Plan

1. Elements of the plan include:

- a. **Persons/groups who will review the data (study team; independent safety monitor):** PI: [name], Medical Monitor: [name], and independent safety monitor
- b. **Plan for safety monitoring and review:**

Adverse Event Definitions and Collection

In this trial, an adverse event (AE) is defined as any untoward or unfavorable medical occurrence in a human subject participant, including any abnormal sign, symptom, or disease, temporally associated with the participant's involvement in the research, whether or not considered related to participation in the research.

A serious adverse event (SAE) is defined as any adverse event that results in:

- Death
- Life-threatening even, a condition that places the study participant at immediate risk of death if they do not seek medical treatment
- Inpatient hospitalization, or prolongation of existing hospitalization
- Permanent disability, defined as the interruption of a study participant's ability to conduct normal life functions

AE's will be collected from the time of consent until the final study visit and will be recorded on an Adverse Event Report Form. At each study visit, study staff will query the participant for any new AE's that may have occurred since the last study visit and will check on the status of any AE's that have not previously resolved.

Adverse Event Assessment

A qualified study clinician will assess all AE's for severity, causality, and expectedness. This assessment will be documented with the medical monitor's signature and date.

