Expectedness refers to the whether the AE is anticipated based on current knowledge of the nature, severity, and frequency of the risks of the study intervention, as defined in the protocol and in the informed consent form. Thus, an event may be listed as a known potential risk, but if the event occurs in a more severe intensity or occurs more frequently than what is known, the event would be considered unexpected.

Adverse Event Reporting

The PI will ensure that all AE's that meet reportability criteria will be reported to the IRB within the expedited IRB-specified timeframe. The KU IRB requires reporting of AE's (whether serious or non-serious) that are determined to be related or probably related to study participation and that were unexpected. The timeframe for reporting AE's/ SAE's that meet these criteria is within five working days of the PI learning of the event. An exception to this timeframe is the reporting of deaths that are determined to be related or probably related to study participation. These must be reported within 24 hours by phone or email, with a full adverse event report submitted within five working days.

Any SAE that is related or probably related to study participation and that is unexpected will also be reported expeditiously to the NIA program officer and to the independent safety officer, within 48 hours of knowledge of the SAE. However, SAE's that result in death that are determined to be related to the study will be reported to the NIA program officer within 24 hours of learning of the event.

A summary of all AE's/ SAE's will be reported to the NIA program officer on a quarterly basis. The PI and medical monitor will also review all AE's/ SAE's on quarterly basis as described below in the Data and Safety Monitoring Plan.

Data and Safety Monitoring Plan

The data and safety monitoring plan consists of oversight by an independent safety monitor.

At the conclusion of each cohort of the study intervention, the study team will provide a report to the independent safety monitor detailing all AE's that have occurred to date. Following the review of safety data, the safety monitor will document his assessment of safety and his determination to: 1) continue the study without any modifications, 2) continue the study, but

only with additional monitoring or other specified modifications to the protocol or 3) discontinue the study due to safety issues.

III. Subject Participation

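### The only scheduled adverse-event query after baseline falls at diet day 70-98 of 84; one question on each of the six existing coaching calls would bring the first query to about day 7-14

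*Combined protocol and SAP*

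**What the plan says.** Section II.E states: "This study will require two study visits". These are baseline, within 30 days before the diet starts, and Week 12 (+/- 2 weeks). Under Visit 2, Check for Adverse Events: "At the Week 12 Visit, study staff will query the participant for any new health conditions that may have arisen since the Baseline Visit". The schedule table marks the adverse-event check in the Week 12 column only.

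Section II.K (Adverse Event Definitions and Collection) gives the general rule: "At each study visit, study staff will query the participant for any new AE's that may have occurred since the last study visit". With two visits, this adds no further query after baseline. The AE definition is broad, "including any abnormal sign, symptom, or disease", and AEs "will be collected from the time of consent until the final study visit".

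Review of what has been collected is in section II.K under Adverse Event Reporting ("The PI and medical monitor will also review all AE's/ SAE's on quarterly basis") and under the Data and Safety Monitoring Plan ("At the conclusion of each cohort of the study intervention, the study team will provide a report to the independent safety monitor").

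The plan has regular contact with participants during the diet. In section II.B, "Counseling will consist of one-on-one sessions with a health coach", by Zoom every two weeks for 12 weeks, six calls per participant, of 15-20 minutes each apart from a longer first one. Group cooking classes run weekly in weeks 1-6, and groceries are provided weekly. No AE question is assigned to any of these contacts.

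**The concern.** Section II.F lists a long series of gastrointestinal symptoms as possible effects of the diet. Such symptoms may start early and be mild enough that a participant does not raise them unasked. Under the present schedule nobody is due to ask until the diet is nearly or completely over. Two things follow.

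- The chance to adapt the diet for that participant has largely passed.
- Onset, duration and severity then rest on recall over many weeks, while the causality grading in section II.K relies on the time sequence of event and exposure.

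The three-cohort design exists so that the intervention can be revised between cohorts, and the pilot is meant to inform a later randomized trial. Dated tolerability data serve both purposes. The gap lies in when the question is asked; the AE definition itself is adequate.

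**Working it through.** **Inputs.** Diet: 12 weeks (section II.B, calls and groceries). Visit 2: 12 weeks +/- 2 weeks (section II.E), counted from diet day 0 as the schedule table does. Calls: six, every two weeks (section II.B). The table marks coaching in weeks 1-6 and 7-11 and leaves Week 12 unmarked. Participants: 30.

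**The plan's own call count.** 12 weeks / 2 = 6 calls, as stated. Spacing: 84 / 6 = 14 days.

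**Present schedule.**
- Diet length: 12 x 7 = 84 days. Visit: 84 +/- 14 = day 70 to 98.
- Diet days left at the first scheduled question: 84 - 70 = 14 (14/84 = 17%), falling to 0 for a visit on day 84 or later.
- Longest recall of a diet-related symptom: 70 to 98 days, or 10 to 14 weeks. (Counted from baseline, up to 30 days more: 98 + 30 = 128.)
- Symptom starting in days 0-14: shortest delay 70 - 14 = 56 days, longest 98 - 0 = 98 days.
- Mean delay with onsets spread evenly (assumption). Visit on day 70, onsets up to then: 70/2 = 35 days. Visit on day 98: 98 - 84/2 = 56 days.

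**With a question on each call.** Scheduled queries after baseline rise from 1 to 7. Call dates are not given, so three placements are shown, the last two consistent with the table and taken with the latest visit, day 98.

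| Call days | Longest recall | Mean delay |
|---|---|---|
| 14, 28, ..., 84 | 14 days | 14/2 = 7 days |
| 7, 21, ..., 77 | 98 - 77 = 21 days | (7 x 3.5 + 70 x 7 + 7 x 17.5)/84 = 637/84 = 7.6 days |
| 0, 14, ..., 70 | 98 - 70 = 28 days | (70 x 7 + 14 x 21)/84 = 784/84 = 9.3 days |

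In the last two rows each product is the number of onset days times the mean wait to the next question. A call on day 0 can find no diet-related event, so the first informative question comes on day 7 or 14, with 84 - 7 = 77 or 84 - 14 = 70 diet days left (92% or 83%).

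**The end of the diet.** AE collection ends at the final visit. If that visit is on day 70 and the diet runs its full length, 84 - 70 = 14 diet days follow closure. A last call on day 70 or 77 still leaves 14 or 7 diet days after it, so the six calls alone do not necessarily cover the tail.

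**The case against.** The best defense is that the plan does not ignore events between visits. AEs that a participant volunteers can be recorded from consent onward, and the expedited reporting rules apply to those that qualify. Participants meet staff at weekly classes in weeks 1-6, exactly the early period of most interest, and speak to a coach who tailors advice to their needs. The food comes from a supermarket, so someone with reflux or bloating can change what they eat without being asked. The coaching script is not in the documents, and an informal health question cannot be ruled out. Serious events are probably rare in a diet pilot that excludes uncontrolled diabetes and hypertension, and without an AE rate the number missed cannot be stated.

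All of this stands and limits the point to scheduled questions. It does not remove it: an opportunity to volunteer a symptom is not a standard question, and none is scheduled before day 70.

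Three stronger readings are tempting and not supported.

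- A reader might infer that the safety monitor would decide wrongly. The monitor reports after each cohort, at about the time of the Week 12 query. Earlier questions would improve the dating of events, but nothing shows a different decision.
- A reader might infer that collection certainly closes while participants are still on the diet. Calls and groceries run for 12 weeks, but acceptability is described as post-intervention and measured at the same visit. The documents do not state outright that the diet continues after an early visit.
- A reader might expect the added question always to give 14-day recall. That requires a call near day 84, which the schedule table does not show.

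**Conclusion.** The point holds as a cheap improvement. There is one scheduled AE query after baseline, when 0-14 of 84 diet days remain. A question on existing calls would cut the longest recall from 70-98 days to about 14-28 days and the mean delay from 35-56 days to about 7-9.3 days. The ranges depend on call dates that the documents do not give, and the mean delays also on evenly spread onsets. The gain is an earlier chance to adapt the diet and better-dated tolerability data for revisions between cohorts and for the planned randomized trial. No primary outcome is invalidated.

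**What to change.** 1. Add one standard question, matched to the section II.K definition, to each of the six one-on-one coaching calls. For example: *Since we last spoke, have you had any new or worse symptom, illness or other health problem?*
2. Record each positive answer with its onset date on the Adverse Event Report Form and send it through the existing assessment. Mark the check in the schedule table for the coaching weeks, and keep the Week 12 check.
3. Keep AE collection open until the later of the final visit and the end of the 84-day diet. If the visit falls before day 84, ask the question at a call on or about day 84.
4. List AEs first found at calls separately from those first found at Week 12, so that the effect of asking more often is visible.

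**Cost.** Asking: 6 x 30 = 180 questions; at an assumed 1-3 minutes each, 3-9 staff hours. Handling, at an assumed 0.5-2 additional AEs per participant (15-60 in all) and 15-30 minutes each: 15 x 15 minutes = 3.75 hours to 60 x 30 minutes = 30 hours. Total: 6.75-39 hours, resting on an AE rate that the documents do not give. If no call falls near day 84, participants seen early need the last call moved or a brief extra one. There is also a short coach script and one protocol amendment (section II.E, schedule table, section II.K). Calls run 1-3 minutes longer, and the recorded AE count will be higher than a single query would give. No new visits or tests are needed.

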The participant may be given a copy of their results related to their blood pressure, blood draw results, and body composition if they request it. The data will not be reviewed by the research team or a physician for the presence of clinically relevant abnormalities.

F. Risk/benefit assessment:

1. **Physical risk**
 - a. Blood draw: Participants May feel soreness, swelling, and bruising at the puncture site during the blood draw. This should go away within a day. Good clinical practice guidelines will be followed for biospecimen sampling.
 - b. DXA: There is always a slight chance of cancer from excessive exposure to radiation. However, given the small amount of radiation used in medical imaging, the benefit of an accurate diagnosis far outweighs the associated risk.
 - c. Food consumption: There is a chance that participants may experience gastrointestinal symptoms when consuming foods on the MIND+SOUL diet including but not limited to: nausea, vomiting, diarrhea, acid reflux, heartburn, indigestion, bloating/excess gas, hiccups, halitosis, cramping, abdominal pain, irritable bowel syndrome, constipation, change in bowel movements, and hemorrhoids, gallstones.
2. **Psychological risk.** There is minimal risk for psychological distress due to the nature of the research topic.
3. **Social risk.** There is minimal risk due to the nature of the research topic.
4. **Economic risk.** There is minimal risk due to the nature of the research topic. Participants

will receive up to \$50 worth of groceries each week (\$600 total) for 12 weeks during the study to offset the cost of healthy foods. Focus group participants will receive a \$25 Visa gift card for their participation.

5. Potential benefit of participating in the study

- a. Individuals participating in this study may feel empowered and valued as part of Alzheimer's prevention in the African American community
- b. To the field of Alzheimer's prevention, community participation of this study will help guide future research in the development of culturally appropriate dietary intervention strategies aimed to reduce the risk of cognitive decline specifically for African Americans

G. Location where study will be performed:

Laboratory tests, educational sessions, and skill-building health education/cooking classes, will take place at the KU ADRC. Counseling sessions will take place via Zoom.

H. Collaboration (with another institution, if applicable):

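### The Week 12 adverse event question is narrower than the protocol's own adverse event definition, and there is no baseline symptom record to compare with

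*Combined protocol and SAP*

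**What the plan says.** Section II.E (Visit 2, Check for Adverse Events) gives a five-minute procedure at Week 12 in which "study staff will query the participant for any new health conditions that may have arisen since the Baseline Visit". The next sentence reads "Adverse event information will be collected and recorded as described in section K".

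Section II.K (Adverse Event Definitions and Collection) defines an adverse event as "any untoward or unfavorable medical occurrence in a human subject participant, including any abnormal sign, symptom, or disease". Events "will be collected from the time of consent until the final study visit". It has its own visit instruction, "At each study visit, study staff will query the participant for any new AE's that may have occurred since the last study visit", and staff "will check on the status of any AE's that have not previously resolved".

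Section II.F, item 1.c, lists the risks of the diet as gastrointestinal symptoms, beginning with "nausea, vomiting, diarrhea, acid reflux, heartburn, indigestion, bloating/excess gas, hiccups".

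At baseline, section II.E (Medical History) records medical conditions and current medications with approximate start dates. No symptom questionnaire appears in the text or in the schedule table. The table marks the adverse event check at Week 12 only.

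**The concern.** The protocol gives two different questions for one check, and the narrower one sits in the visit procedure that staff are likely to follow on the day. A participant asked about new conditions may not think to mention bloating, reflux or constipation. Every participant also enters with at least one cardiovascular risk factor (section II.D, inclusion d), and worsening of such a condition is not new in the ordinary sense.

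The trial has one arm, so a participant's own baseline is the only comparison for tolerability. Severity, causality and expectedness are assessed only for events that have been elicited. The counts feed the report to the independent safety monitor after each cohort and the quarterly summary to the funder. Section II.C also allows revisions between cohorts. If symptoms are under-elicited, the diet looks better tolerated than it is, in data meant to support a larger trial.

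**Working it through.** No sample size, power or event-rate figure is involved. The check is a comparison of text, plus the length of the recall period.

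**Side by side**

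| Feature | II.E, Week 12 check | II.K |
|---|---|---|
| Content | New health conditions | Any untoward occurrence, with signs and symptoms included |
| Start point | Baseline Visit | Consent |
| Open events | Not mentioned in the question | Status checked |
| Worsening of an existing condition | Not named | Not named, though the general definition can cover it |
| When asked | Week 12 (schedule table) | Each study visit |

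The start points differ only when consent is remote. Section II.B allows remote consent a few days before baseline; otherwise consent is on the baseline day. The status check in II.K applies to adverse events already recorded, so it does not pick up worsening of a condition that was present at entry.

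**Where the gap falls.** Item 1.c of II.F names 16 complaints. Three are diagnoses that a participant would naturally call a condition (irritable bowel syndrome, hemorrhoids, gallstones). That leaves 16 − 3 = 13 symptoms, or 12 if acid reflux is counted as a condition. The narrower wording therefore fits poorly with most of the diet's named risks.

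**Recall period.** Inputs, all from II.E: baseline falls within 30 days before the diet starts, and the final visit is at week 12 with a window of 2 weeks either way. In days, 12 × 7 = 84 and 2 × 7 = 14. Assuming that week 12 is counted from diet start:

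- Shortest: 84 − 14 + 0 = 70 days.
- Nominal, with baseline on the day the diet starts: 84 days.
- Longest: 84 + 14 + 30 = 128 days, about 18 weeks.

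If week 12 were counted from the Baseline Visit instead, the range would be 84 − 14 = 70 to 84 + 14 = 98 days.

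**Other places where symptoms could surface.** The cooking classes (section II.B, weekly for 6 weeks) and the coaching calls (6 per participant) are described without an adverse event query. The listed domains of the first acceptability survey do not include symptoms. A complaint that a participant volunteers would still fall within section K's collection period, but no one is instructed to ask for it between the two visits.

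**The case against.** The strongest reply is the cross-reference. The sentence after the Week 12 question sends staff to section K for collection as well as recording, and section K has its own query for any new adverse event under a definition that includes symptoms. This stands. A reader might infer that the Week 12 check asks about new conditions and nothing else, so that bowel symptoms and worsening will be missed. The documents do not support that: read together, they do instruct staff to ask about symptoms and to follow up open events. What the reply leaves unresolved is that section K's query uses a technical term that staff must put into plain words, and the Week 12 procedure is the only place that does so, too narrowly.

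Other replies also have force:

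- Neither section is a verbatim script, and nothing in the documents shows how participants interpret the question.
- Baseline conditions carry approximate start dates, and a participant can be asked when a symptom began. A symptom's onset is therefore not unknowable, but dating it depends on memory.
- The consent-to-baseline gap is short and comes before the diet starts.
- Causality is judged event by event, so lost events do not distort the judgement on those captured. The documents also give no known frequency for the listed symptoms against which expectedness could shift.
- Adverse event rates are not a stated primary or secondary outcome.
- Prompting from a list draws out background symptoms that a single-arm trial cannot attribute. Asking the same list at baseline controls this in part, not fully.

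**Conclusion.** The two sections differ in content and start point and should be reconciled. Under-capture of gastrointestinal symptoms and of worsening conditions is a risk if staff follow the visit wording alone; the documents do not show that it will happen. No undercount can be calculated, because the documents give neither the frequency of symptoms nor the share that each question would elicit.

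What can be stated is that one scheduled five-minute check covers roughly 70 to 128 days, on the assumption that week 12 runs from diet start. Because no symptom inventory is taken at baseline, the judgement that a symptom is new or worse rests on recall over that period. Aligning the two wordings would not cure this second gap, since section K adds no baseline symptom record either. The point is worth acting on because the correction is cheap and tolerability is central to a dietary pilot. It does not threaten the trial's primary feasibility and acceptability aims.

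**What to change.** 1. Reword the Week 12 check in II.E to match section K: any new or worsened sign, symptom or condition since consent, plus the status of open events. Name worsening in section K as well.
2. Ask the symptoms listed in II.F, item 1.c, in the same words at baseline and at Week 12. Report, by cohort and overall, the number of participants with each symptom new or worse than at baseline.
3. Reconcile the schedule table, which has the check at Week 12 only, with section K's query at each study visit.

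The cost is about five minutes per visit: 2 × 5 = 10 minutes per participant, or 30 × 10 = 300 minutes (5 hours) across the trial. More mild events will need recording and assessment, and prompting will elicit some background symptoms, which the baseline administration offsets only in part. The intervention and the other assessments are unchanged.
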